### 7.6 Safety

#### 7.6.1 Adverse Events

Adverse events are assessed using the NCI Common Terminology Criteria for Adverse Events (CTCAE) v4.0 handbook and those with grade 2 or higher are recorded on the baseline report, 30 day follow-up report, and 90 day follow-up report. Events reported on 30 day follow-up report will be summarized respectively for patients who were randomized to RT+BSC arm and received radiotherapy and who were randomized to BSC. Events reported on 30 day follow-up report will be summarized by the following three groups: (1) patients who were randomized to RT+BSC arm and received radiotherapy; (2) patients who were randomized to BSC and crossed over to RT+BSC; (3) patients who were randomized to BSC but not crossed over to RT+BSC.

Radiotherapy related adverse events are those events with a relation to protocol therapy of 3=possible, 4=probable or 5=definite.

Severe adverse events are those events reported with a CTCAE Grade of 3 or higher.

- Grade 2 or higher adverse events at days 30 and days 90: CTCAE grade per patient (**Table 29**)
- Grade 2 or higher radiotherapy related adverse events at days 30 and days 90: CTCAE grade per patient (**Table 31**)
- Severe adverse events at days 30 and 90: CTCAE grade per patient (**Table 32**)

Proportions of patients experiencing any grade  $\geq 2$  adverse event at day 30 and day 90 will be compared between treatment arms is conducted by a stratified CMH test (**Table 30**).

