The Princess Margaret Cancer Centre study investigated 41 patients with diffuse HCC (21) or liver metastases (20, 50% from a gastrointestinal primary site) who had pain (27), discomfort (6) or other (5) symptoms [*Soliman 2013*]. The use of 8 Gy in one fraction to the whole (or near whole) liver, with an anti-emetic to prevent nausea, resulted in a clinically meaningful improvement in average index symptom intensity assessed using the BPI in 48% (95% CI: 28-68%) of patients one month following RT with no differences between patients with HCC and liver metastases. In patients with pain or abdominal discomfort as their index symptom, pain relief tended to occur within a few days and was sustained with a clinically significant improvement at one month in 55% (95% CI: 32-76%) of patients when evaluating “average” pain/discomfort, and in 59% (95% CI: 36-79%) when evaluating “worst” pain/discomfort in the past 24 hours. The pathophysiology of pain relief is not clearly understood; however objective tumour shrinkage is not required for effective pain relief. There was no reduction in symptoms in patients who had nausea or fatigue as their index symptom. RT treatment was well tolerated. Grade 1 or 2 fatigue, often present at baseline, was common; grade 1 or 2 nausea was seen in 3 patients, and grade 2 gastritis was seen in 1 patient. One patient, who declined anti-emetics prior to RT, developed grade 3 vomiting. There was no other reported toxicity. From a QoL perspective, the benefits were less. Twenty-nine percent (95% CI: 8 – 45%) of patients treated with RT had a significant improvement in FACT-HBS at 30 days and 25% (95% CI: 10- 47%) of patients had significant improvement in FACT- TOI at 30 days. Based on the results of this pilot study, the next logical step is to test, in a multi-institutional randomized study, that RT may lead to a clinically significant hepatic pain reduction and QoL improvement in a greater proportion of patients compared to BSC alone [*Hoyer 2012*].

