5.1.6 Patient reports moderate or severe pain/discomfort prior to the baseline evaluation and this pain is considered “stable” over a period of up to 7 days prior to randomization (see Appendix III for full details);

Definition of moderate pain:

Patient reports level of 4-6 (on a BPI scale from 0 to 10) pain or discomfort “at its worst in the past 24 hours”, occurring in the right upper quadrant of the abdomen, the upper abdomen and/or referred to the right shoulder, attributable to liver cancer.

Definition of severe pain:

Patient reports level of 7-10 (on a BPI scale from 0 to 10) pain or discomfort “at its worst in the past 24 hours”, occurring in the right upper quadrant of the abdomen, the upper abdomen and/or referred to the right shoulder, attributable to liver cancer.

Definition of “stable” pain:

Patient must show moderate or severe “stable” pain by reporting a score of 4 or greater (on 2 separate days within the 7 day period prior to randomization) with the difference of these scores being 0, 1, 2 or 3.

5.1.7 Patient reports moderate or severe pain (i.e. pain score is 4 or higher). This baseline score must also be stable compared to the most recent pre-baseline pain score with the difference between these scores being 0, 1, 2, or 3 (see Appendix III for full details).

5.1.8 Blood work obtained within 14 days prior to randomization as follows:

- Hemoglobin > 70 g/L;
- Platelets > 25 x 10⁹/L;
- Absolute neutrophil count (ANC) > 1.0 x 10⁹/L;
- INR < 3;
- Bilirubin < 2.5 UNL (except for subjects with Gilbert’s Disease who are eligible despite elevated serum bilirubin level);
- AST or ALT < 10 x UNL.

5.1.9 Eastern Cooperative Oncology Group (ECOG) performance status (PS) 0-3 within 14 days of Randomization (see Appendix II).

5.1.10 Life expectancy of > 3 months.

5.1.11 18 years of age or older at the time of randomization.

5.1.12 Patient is willing to complete the Pre-Baseline Pain/Discomfort Questionnaire and the Pain/Discomfort and Medication Questionnaire in English, French or other validated language (please contact the HE.1 Study Coordinator). The baseline assessment must be completed within required timelines prior to randomization. Unwillingness to complete the Pre-Baseline Pain/Discomfort Questionnaire and Pain/Discomfort and Medication Questionnaire will make the patient ineligible for the study.

AMEND #1: 2018-JUL-31

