Baseline Analgesia Assessment	
 Pain/Discomfort and Medication Questionnaire 	Following the completion of the last Pre-Baseline Pain/Discomfort Questionnaire that defined stability and on or prior to the date of randomization
Adverse Events*	
 Baseline adverse event evaluation (to document residual adverse event from previous therapy and baseline symptoms) 	Following the completion of the last Pre-Baseline Pain/Discomfort Questionnaire that defined stability and on or prior to the date of randomization
Quality of Life	
 FACT-Hep 	Following the completion of the last Pre-Baseline Pain/Discomfort Questionnaire that defined stability and on or prior to the date of randomization
Other Assessments	
 Pregnancy test which may include an ultrasound to rule out pregnancy (for women of child bearing potential only) 	≤ 14 days prior to randomization
Correlative Studies	
 Blood draw for correlative studies (for consenting patients only) 	≤ 14 days prior to randomization

* Adverse events will be graded using the NCI Common Terminology Criteria for Adverse Events (CTCAE) (Appendix VII). Only AEs deemed grade ≥ 2 are required to be reported.

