The major adverse effects are expected to be related to underlying disease and from analgesia use. The most likely toxicities from analgesia use and/or underlying cancer and/or liver disease are confusion, fatigue, nausea, vomiting, constipation, encephalopathy, insomnia, and decline in liver function.

In addition to the above toxicities, radiation related toxicities may occur such as anorexia, nausea, vomiting, diarrhea, fatigue, gastritis, esophagitis or duodenitis. It is possible that a pain flare and worsening of liver function may occur within the first 2-3 days post RT.

Adverse events will be graded using the NCI Common Terminology Criteria for Adverse Events (CTCAE) (Appendix VII).

8.3.5 *Duration of Therapy (Arm 2)*

Patients will be followed for 90 days post-randomization.

8.3.6 *Patient Compliance (Arm 2)*

Pain/Discomfort and Medication Questionnaire and FACT-Hep QoL compliance will be measured at baseline, 30 days and 90 days.

In addition, the Pain/Discomfort and Medication Questionnaire will record analgesia use from the past 24 hours at baseline, 30 days and 90 days.

8.4 *Radiation Treatment Plan*

The radiation therapy plan is designed to deliver 8 Gy in one fraction to the symptomatic liver cancer. This will require whole (or near whole) liver irradiation, generally using simple techniques such as an oblique or anterior-posterior parallel pair beam arrangement (see Appendix VIII).

8.4.1 *Patient Evaluation*

Patients must be able to lie supine for the duration of treatment (e.g. 30 minutes).

8.4.2 *Equipment and Treatment Delivery*

8.4.2.1 *Equipment*

Treatment is to be delivered using 4-18 MV photons.

8.4.2.2 *Treatment Delivery*

3D conformal radiation or IMRT, with multi-leaf collimators, blocks or wedges is permitted.

8.4.3 *Positioning, Immobilization and Localization/Simulation*

8.4.3.1 *Positioning*

Patients will be positioned supine with arms above their head. If not possible, one or both arms at the sides is permitted, although this will require care to avoid irradiation through the arms.

8.4.3.2 *Immobilization*

Use of chest board or vacuum lock bag is recommended, in combination with calf and knee supports. For anterior-posterior beam arrangements, no such devices are required.

8.4.3.3 *Localization Imaging/Simulation*

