**Table 12: Baseline Grade 2 or Higher Adverse Events**

Data set: All Randomized Patients									
	Number of patients (%)								
	RT+BSC N=**			BSC N=**			Total N=**		
	Grade			Grade			Grade		
	2	3	4	2	3	4	2	3	4
Patients with any AE	** (**)	** (**)	** (**)	** (**)	** (**)	** (**)	** (**)	** (**)	** (**)
Patients with AE within category	**(**)	**(**)	**(**)	**(**)	**(**)	**(**)	**(**)	**(**)	**(**)
Category 1 	**(**)	**(**)	**(**)	**(**)	**(**)	**(**)	**(**)	**(**)	**(**)
Event 1	**(**)	**(**)	**(**)	**(**)	**(**)	**(**)	**(**)	**(**)	**(**)
Event 2	**(**)	**(**)	**(**)	**(**)	**(**)	**(**)	**(**)	**(**)	**(**)
Event 3	**(**)	**(**)	**(**)	**(**)	**(**)	**(**)	**(**)	**(**)	**(**)
...	**(**)	**(**)	**(**)	**(**)	**(**)	**(**)	**(**)	**(**)	**(**)
Category 2 	**(**)	**(**)	**(**)	**(**)	**(**)	**(**)	**(**)	**(**)	**(**)
Event 1	**(**)	**(**)	**(**)	**(**)	**(**)	**(**)	**(**)	**(**)	**(**)
...	**(**)	**(**)	**(**)	**(**)	**(**)	**(**)	**(**)	**(**)	**(**)

(1) Patients may have more than one event within a category.

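### The between-arm adverse event comparison (SAP 7.6.1, Table 30) ignores the baseline report, so grade 2 or higher events already present at entry reduce its sensitivity to new harm from RT

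*SAP*

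**What the plan says.** SAP 7.6.1 plans one adverse event comparison with a p-value: the proportion with any grade 2 or higher "adverse event at day 30 and day 90 will be compared between treatment arms is conducted by a stratified CMH test". Table 30 sets it out for all treated patients, with one row for day 30 and one for day 90. Neither place requires an event to be new or worse than at entry. Protocol 10.1.1 makes patients evaluable for adverse events from randomization and adds no such rule.

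The baseline information exists. SAP 7.6.1 states that adverse events are graded and "those with grade 2 or higher are recorded on the baseline report, 30 day follow-up report, and 90 day follow-up report". The table in Protocol 6.0 describes the purpose of the first of these reports: "Baseline adverse event evaluation (to document residual adverse event from previous therapy and baseline symptoms". The SAP uses it only in a descriptive listing, "Table 12: Baseline Grade 2 or Higher Adverse Events".

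The protocol also describes a population with many symptoms. Criterion 5.1.7 reads "Patient reports moderate or severe pain (i.e. pain score is 4 or higher"). ECOG 3 and Child-Pugh C10 are allowed. For the RT arm, Protocol 8.3.4 says "The major adverse effects are expected to be related to underlying disease and from analgesia use", and 8.2.4 says much the same for BSC. On the phase II study, Protocol 2.4 reports "Grade 1 or 2 fatigue, often present at baseline, was common; grade 1 or 2 nausea was seen in 3 patients".

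**The concern.** A yes/no endpoint that a patient already meets at entry cannot register a new event in that patient. In this population some patients will have grade 2 or higher fatigue, nausea or other disease symptoms before randomization. If these persist and are reported again at day 30 or day 90, they count in both arms. Randomization balances them in expectation, so they do not bias a comparison under no effect, but they compress the difference that RT toxicity can produce.

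A second mechanism is conditional. If the index liver pain is itself entered as a grade 2 or higher adverse event, a patient whose pain is relieved by RT may drop out of the count, and part of the efficacy result would enter the safety row.

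At stake is how a small or null difference in Table 30 would be read. It could be taken as evidence that RT adds little harm when the measure had little ability to show it.

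**Working it through.** The documents give no planning figure for the safety comparison, so there is none to reproduce. They also give no rate of baseline or new events; the rates below are assumptions shown over a range. The figures suit day 30 best, because BSC patients may cross over to RT after that.

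**1. Dilution.** Let b be the share of patients in each arm with a persisting baseline grade 2 or higher event that is recorded again at follow-up. Let c and t be the risks of a new event on BSC and RT, independent of b. Table 30 then shows b + (1 − b)c against b + (1 − b)t, a difference of (1 − b)(t − c).

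Take c = 10% and t = 40%. Take 33 patients per arm, that is, the 66 randomized patients in SAP 2.3 split evenly; the treated set may be smaller. Power uses the two-sided 5% normal approximation, Φ{[d√n − 1.96√(2p̄(1 − p̄))] / √[p₁(1 − p₁) + p₂(1 − p₂)]}, where d is the difference and p̄ the mean of the two proportions.

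| b | BSC | RT+BSC | Difference | Power |
|---|---|---|---|---|
| 0% | 10% | 40% | 30 points | 82% |
| 50% | 55% | 70% | 15 points | 24% |
| 70% | 73% | 82% | 9 points | 14% |
| 90% | 91% | 94% | 3 points | 7% |

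**2. What a new-or-worsened count recovers.** Suppose RT causes a new event in 20% of patients who would otherwise have none.

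- No new events on BSC: 0% v 20%, power 79%.
- 10% of BSC patients have a new event: RT is 1 − 0.90 × 0.80 = 28%, a difference of 18 points, power 46%.
- 30% of BSC patients have a new event: RT is 1 − 0.70 × 0.80 = 44%, a difference of 14 points, power about 21%.
- For contrast, the second case under the any-event count at b = 50%: 0.50 + 0.50 × 0.10 = 55% v 0.50 + 0.50 × 0.28 = 64%, a difference of 9 points, power about 11%.

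**3. Pain offset, only if index pain is recorded as an event.** SAP 5 plans pain response of 5% (BSC) and 40% (RT), so 95% and 60% are non-responders. Let q be the share of non-responders whose pain is recorded as grade 2 or higher, and assume every responder falls below grade 2. With h the risk of a new RT event, BSC shows 0.95q and RT shows 1 − (1 − 0.60q)(1 − h). The two are equal when h = 1 − (1 − 0.95q)/(1 − 0.60q).

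| q | h at which the arms look equal |
|---|---|
| 0 | 0% |
| 0.25 | 10% |
| 0.50 | 25% |
| 0.75 | 48% |
| 1 | 87.5% |

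For scale, the gastrointestinal events named in Protocol 2.4 are at most (3 + 1 + 1)/41 = 12%, taking every nausea case as grade 2 and no overlap between patients. That rate would be masked at q of about 0.29. Neither document gives q, and q = 0 is possible.

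**The case against.** - **The endpoint is compared as worded.** The objective in Protocol 1.2 and SAP 3.2 is the proportion with grade 2 or higher events at 30 and 90 days, and Table 30 compares exactly that. This stands. A reader might infer that the objective goes unanswered; it does not. The complaint is about sensitivity.
- **Toxicity is shown elsewhere.** Tables 29 and 32 give counts by event and grade, and their notes promise the same for BSC. Nausea, vomiting and gastritis will therefore be visible by arm, next to Table 12. This stands in part: marginal counts do not show which patients changed from baseline, and the shells carry no test. Table 31 has no BSC column at day 30 because those patients have had no protocol RT, which is not a fault.
- **A reversal is not established.** A reader might infer that Table 30 would make RT look safer while it causes more new toxicity. With the protocol's 45% pain response, new events of 10% v 40% and all unrelieved pain recorded, the arithmetic is 1 − 0.05 × 0.90 = 95.5% on BSC v 1 − 0.45 × 0.60 = 73.0% on RT. The documents do not support this as an expectation. They do not say that index pain is coded as an adverse event, and they list pain assessment and adverse events as separate items. The example sets q = 1, leaves out all other background events and assumes every responder drops below grade 2, although a fall from 9 to 7 is a response that still meets the definition of severe pain in Protocol 5.1.6. The SAP's 40% response gives 76.0% instead of 73.0%.
- **The remedy is partial.** Protocol 8.2.4 expects disease-related events, including decline in liver function, on BSC. New ones stay in any new-or-worsened count. This stands, and is why 46% rather than 79% is the fairer figure for the 20% case.
- **Laboratory tables.** Tables 13 to 15 already give baseline grades by arm, and nothing says laboratory grades feed Table 30. Shift tables are therefore optional.

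**Conclusion.** The point holds as a loss of sensitivity. Table 30 makes no use of baseline events that the trial collects, and the observed difference shrinks by the factor 1 − b. For an assumed true difference of 30 points this leaves 15, 9 or 3 points at b = 50%, 70% or 90%. The result rests on three assumptions: persisting baseline events are recorded again at follow-up, they are equally common in the two arms, and they are independent of new events. The documents do not define whether an event at day 30 means one present at the visit or any since randomization, but neither reading removes a persisting baseline event.

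The effect of pain relief on the count is only a possibility. Its size and the direction of the net result depend on how index pain is coded, which neither document states. It is therefore not supported to say that the comparison mainly measures disease and pain relief, or that RT will appear safer than it is.

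**What to change.** Keep the any-event rows of Table 30 unchanged, since they are the listed protocol endpoint. Add to SAP 7.6.1 and Table 30 a supplementary row at each time point: patients with at least one grade 2 or higher event that is new, or of higher grade than the same CTCAE term on that patient's baseline report. Test it with the same CMH test stratified by HCC versus liver metastases. Show it with and without index abdominal pain; both are needed because Protocol 8.3.4 names pain flare as a possible RT effect. State whether index pain is recorded as an adverse event. Shift-from-baseline grades in Tables 33 to 35 would be a useful option.

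The cost is SAP wording and programming; baseline and follow-up events are already on the report forms. Because the trial is open-label and accrual has closed, the row should be dated and labelled supplementary.

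Two limits should be stated with the result. Grade 1 events are not recorded at baseline, so a change from grade 1 to 2 counts as new in both arms. New disease-related events on BSC remain in the count and limit the gain in power.

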### **7.6.2 Laboratory Evaluations**

Laboratory evaluations reported on the follow-up report 30 day visit and follow-up report 90 day will be classified according to the CTCAE if possible. Laboratory tests that are not covered by the CTCAE grading system will be summarized according to the following categories: normal and abnormal. Tabulations of laboratory adverse events will be presented by groups similarly as the adverse events.

#### **7.6.2.1 Hematology**

- Hemoglobin and platelets at days 30 and 90: CTCAE grade per patient (**Table 33**)

#### **7.6.2.2 Serum Chemistry**

- Total bilirubin, AST, ALT, albumin, serum creatinine, alpha-fetoprotein at days 30 and 90: CTCAE grade per patient (**Table 34**)

#### **7.6.2.2 Coagulation**

- INR at days 30 and 90: CTCAE grade per patient (**Table 35**)

## **7.7 Pre-medication, Concomitant Medications and Other Anti-Cancer Treatments**

Patients who received RT may receive pre-medications before the RT. Treated patients may receive concomitant medications or other anti-cancer treatments during the whole study. Tabulations of pre-medications, concomitant medications and other anti-cancer treatments will be presented for both arms.

- Pre-medications for patients who received RT (**Table 36**)
- Concomitant medications for all randomized patients (**Table 36**)
- Anti-cancer treatments for patients before 30 days after randomization, by treatment group (**Table 37**)
- Anti-cancer treatments for all patients between 30 and 90 days after randomization, by treatment group (**Table 37**)

## **7.8 Quality of Life**

Patient-reported QoL in this study is assessed at baseline and on days 30 and 90 from randomization by using Functional Assessment of Cancer Therapy-Hepatobiliary (FACT-Hep) questionnaire. The following are the scoring algorithms for this instrument.

### 7.8.1 FACT-Hep

The FACT-Hep questionnaire is a 45-item instrument consisting of the 27-item cancer-specific QoL instrument FACT-G and a site-specific 18-item hepatobiliary subscale (HBS). The FACT-G consists of four subscales: (1) physical well-being (PWB); (2) social and family well-being (SFWB); (3) emotional well-being (EWB); and functional well-being (FWB). The FACT-Hep Trial Outcome Index (TOI) is the sum of the PWB, FWB, and HBS subscales. Individual scores for each subscale, FACT-G score, the trial outcome index (TOI), and the total FACT-HEP score will be scored according to FACT-Hep Scoring Guidelines as below with a subscale in which less than half of the items are completed treated as missing. The higher the score, the better the QoL.

- PWB subscale score =  $(28-GP1-GP2-CP3-GP4-GP5-GP6-GP7) * 7 / (\text{number of items answered})$
- SFWB subscale score =  $(GS1+GS2+CS3+GS4+GS5+GS6+GS7) * 7 / (\text{number of items answered})$
- EWB subscale score =  $(20-GE1+GE2 -GE3-GE4-GE5-GE6) * 6 / (\text{number of items answered})$
- FWB subscale score =  $(GF1+GF2+CF3+GF4+GF5+GF6+GF7) * 7 / (\text{number of items answered})$
- HBS subscale score =  $(56-C1-C2+C3+C4-C5+C6-Hep1-Cns7-Cx6-HI7+An7-Hep2-Hep3-Hep4-Hep5-Hep6-HN2-Hep8) * 18 / (\text{number of items answered})$
- FACT-G score = PWB score + SFWB score + EWB score + FWB score
- FACT-TOI = PWB subscale score + FWB subscale score + HBS subscale score
- FACT-HEP score = PWB score + SFWB score + EWB score + FWB score + HBS score

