If a particular question has not been answered, please document the reason(s) in the appropriate space on the questionnaire. If the whole questionnaire has not been completed, please document the reason(s) on the appropriate case report forms.

2. Pre-treatment Assessment

It should be explained to the patient that the purpose of the questionnaire is to assess the impact of treatment on different areas of the patient's life, e.g.: psychological distress, social disruption, side-effects, et cetera.

The CRA should collect the questionnaire as soon as it has been completed, check to see that each question has been answered and gently remind the patient to answer any inadvertently omitted questions. If a patient states that s/he prefers not to answer some questions and gives a reason(s), the reason(s) should be noted on the questionnaire. If a specific reason is not given, this also should be noted on the questionnaire.

3. Assessments on Day 30 and Day 90

The quality of life questionnaire should be given to the patient before being seen by the doctor. If the patient does not have a doctor visit scheduled, or if it was not possible for the patient to complete the questionnaire before being seen by the doctor, s/he should still complete the questionnaire.

A patient may, on occasion, be reluctant to complete the questionnaire because they feel unwell. In that case, you may express sympathy that things are below par, but state that this is exactly the information we require if we are to understand more about how quality of life is affected. You may also remind them that it takes only a few minutes to complete.

It defeats the whole purpose of the assessment if it is delayed until the patient feels better!

5. What If . . .

The patient should complete the questionnaires at the clinic. The exception is that the design of some trials may require the patient to take the questionnaire home with them after leaving the clinic, and complete it on the specific day, because a return visit to the clinic is not scheduled.

There may be circumstances when the patient does not complete the questionnaire as required in the clinic. Three situations are described below. In these cases, it is beneficial if quality of life data can still be collected.

- A. The patient leaves the clinic before the questionnaire could be administered, or someone forgets to give the questionnaire to the patient.

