GP1	I have a lack of energy	0	1	2	3	4
GP2	I have nausea	0	1	2	3	4
GP3	Because of my physical condition, I have trouble meeting the needs of my family	0	1	2	3	4
GP4	I have pain	0	1	2	3	4
GP5	I am bothered by side effects of treatment	0	1	2	3	4
GP6	I feel ill	0	1	2	3	4
GP7	I am forced to spend time in bed	0	1	2	3	4

SOCIAL/FAMILY WELL-BEING

		Not at all	A little bit	Some- what	Quite a bit	Very much
--	--	---------------	-----------------	---------------	----------------	--------------

		0	1	2	3	4
GS1	I feel close to my friends	0	1	2	3	4
GS2	I get emotional support from my family	0	1	2	3	4
GS3	I get support from my friends	0	1	2	3	4
GS4	My family has accepted my illness	0	1	2	3	4
GS5	I am satisfied with family communication about my illness	0	1	2	3	4
GS6	I feel close to my partner (or the person who is my main support)	0	1	2	3	4
Q1	Regardless of your current level of sexual activity, please answer the following question. If you prefer not to answer it, please mark this box  and go to the next section.					
GS7	I am satisfied with my sex life	0	1	2	3	4

FACT-Hep (Version 4)

Please circle or mark one number per line to indicate your response as it applies to the past 7 days.

EMOTIONAL WELL-BEING

GE1
GE2
GE3
GE4
GE5
GE6

		Not at all	A little bit	Some- what	Quite a bit	Very much
GE1	I feel sad	0	1	2	3	4
GE2	I am satisfied with how I am coping with my illness	0	1	2	3	4
GE3	I am losing hope in the fight against my illness	0	1	2	3	4
GE4	I feel nervous	0	1	2	3	4
GE5	I worry about dying	0	1	2	3	4
GE6	I worry that my condition will get worse	0	1	2	3	4

FUNCTIONAL WELL-BEING

GF1
GF2
GF3
GF4
GF5
GF6
GF7

		Not at all	A little bit	Some- what	Quite a bit	Very much
GF1	I am able to work (include work at home)	0	1	2	3	4
GF2	My work (include work at home) is fulfilling	0	1	2	3	4
GF3	I am able to enjoy life	0	1	2	3	4
GF4	I have accepted my illness	0	1	2	3	4
GF5	I am sleeping well	0	1	2	3	4
GF6	I am enjoying the things I usually do for fun	0	1	2	3	4
GF7	I am content with the quality of my life right now	0	1	2	3	4

FACT-Hep (Version 4)

Please circle or mark one number per line to indicate your response as it applies to the past 7 days.

ADDITIONAL CONCERNS		Not at all	A little bit	Some-what	Quite a bit	Very much
C1	I have swelling or cramps in my stomach area	0	1	2	3	4
C2	I am losing weight	0	1	2	3	4
C3	I have control of my bowels	0	1	2	3	4
C4	I can digest my food well	0	1	2	3	4
C5	I have diarrhea (diarrhoea)	0	1	2	3	4

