### **7.8.5 Proportion of Patients with Clinically Significant Improvement in QOL**

A clinically significant improvement in QOL is defined by  $\geq 5$  points change in the Functional Assessment of Cancer Therapy (FACT) Hepatobiliary Subscale (FACT-HBS) and Trial Outcome Index (FACT-TOI) from baseline. Proportions of patients who had clinically significant improvement in QoL from baseline to day 30 and day 90 are summarized in **Table 41** and compared by a stratified CMH test adjusting for the stratification factor (HCC versus liver metastases) (**Table 41** ).

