**Table 41: Proportion of Patients with Clinically Significant Improvement in QoL**

	RT+BSC N (%)	BSC N (%)	CMH P-value (*)
Patients with QoL at baseline and day 30			
With Clinically significant improvement (**) in QoL	**	**	**
≥5 point change in FACT-HBS	** (**, **)	** (**, **)	0.***
≥5 point change in FACT-TOI	** (**, **)	** (**, **)	0.***
With Clinically significant improvement (**) in QoL	** (**, **)	** (**, **)	0.***
≥5 point change in FACT-HBS	** (**, **)	** (**, **)	0.***
≥5 point change in FACT-TOI	** (**, **)	** (**, **)	0.***
Patients with QoL at baseline and day 90			
With Clinically significant improvement (**) in QoL	**	**	
≥5 point change in FACT-HBS	** (**, **)	** (**, **)	0.***
≥5 point change in FACT-TOI	** (**, **)	** (**, **)	0.***

\* Stratified Cochran-Mantel-Haenszel test adjusting for the stratification factor (HCC versus liver metastases)

\*\* ≥5 point change in both FACT-HBS and FACT-TOI

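### The SAP's printed PWB, EWB and HBS formulas mis-score, or lose, any FACT-Hep subscale with a blank reverse-scored item

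*SAP*

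**What the plan says.** SAP section 7.8.1 sets out the FACT-Hep scoring. Three of the five subscales contain reverse-scored items, and each starts from a fixed constant:

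- PWB: "28-GP1-GP2-CP3-GP4-GP5-GP6-GP7) * 7" divided by the number of items answered.
- EWB: "20-GE1+GE2 -GE3-GE4-GE5-GE6) * 6" divided by the number answered.
- HBS: "56-C1-C2+C3+C4-C5+C6-Hep1-Cns7-Cx6-HI7+An7-Hep2-Hep3-Hep4-Hep5-Hep6-HN2-Hep8", multiplied by 18 and divided by the number answered.

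The same section keeps partly answered subscales unless too few items are present, "with a subscale in which less than half of the items are completed treated as missing". It does not say how a blank item enters the bracket.

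Protocol Appendix IX expects some blanks. Staff check the form and remind the patient, but also record the reason "If a patient states that s/he prefers not to answer some questions". The questionnaire's cover page asks whether every question was answered and, if not, why.

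The scores feed SAP section 7.8.5 ("Proportions of patients who had clinically significant improvement in QoL from baseline to day 30 and day 90 are summarized in" Table 41), where the cut-off is 5 points on HBS and on TOI, for example "≥5 point change in FACT-HBS". TOI is the sum of PWB, functional well-being (FWB) and HBS.

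**The concern.** The proration factor and the half-items rule show that these formulas are meant for partly answered forms, yet on those forms they break. The constant still holds four points for every reverse-scored item, answered or not. A patient who skips a symptom item is therefore scored as if free of that symptom, and the inflated total is then multiplied up. The other literal reading, in which any blank makes the whole expression missing, discards subscales that the SAP says to keep.

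HBS and TOI responder proportions at days 30 and 90 are named secondary endpoints. Under the first reading, more blanks at follow-up than at baseline can create false responders, and more blanks at baseline can hide real ones. Under the second, patients drop out of an already small comparison: 66 were randomized and 42 were evaluable for the day 30 pain endpoint (SAP section 2.3). If about 21 per arm contribute QoL data (an assumption), one misclassified patient moves an arm's proportion by 1/21, or about 5 percentage points.

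**Working it through.** **Inputs.** Item counts come from the printed formulas in SAP 7.8.1. The 0 to 4 response range comes from the questionnaire in Protocol Appendix IX.

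| Subscale | Items n | Reverse-scored | Positively worded | Constant | Maximum |
|---|---|---|---|---|---|
| PWB | 7 | 7 | 0 | 28 | 28 |
| EWB | 6 | 5 | 1 (GE2) | 20 | 24 |
| HBS | 18 | 14 | 4 (C3, C4, C6, An7) | 56 | 72 |

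**Complete forms.** The constants equal 4 × 7 = 28, 4 × 5 = 20 and 4 × 14 = 56. With every item answered, the printed formula equals the sum of (4 − x) over reverse-scored items plus x over positive items. The plan's figures are therefore right for complete forms.

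**Reading (a): blanks left out of the bracket.** Suppose k reverse-scored items are blank and all other items are answered.

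- Printed score: [constant − Σ answered reverse x + Σ positive x] × n/(n − k)
- Correct prorated score: [Σ answered reverse (4 − x) + Σ positive x] × n/(n − k)
- Difference: 4k × n/(n − k), whatever the answers

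| Excess | k = 1 | k = 2 | k = 3 |
|---|---|---|---|
| PWB | 4 × 7/6 = 4.67 | 8 × 7/5 = 11.2 | 12 × 7/4 = 21.0 |
| EWB | 4 × 6/5 = 4.8 | 8 × 6/4 = 12.0 | 12 × 6/3 = 24.0 |
| HBS | 4 × 18/17 = 4.24 | 8 × 18/16 = 9.0 | 12 × 18/15 = 14.4 |

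On 20,000 random forms per subscale with one and two blanks, the difference equalled these values every time. One blank in each of PWB and HBS adds 4.667 + 4.235 = 8.90 to TOI.

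Two examples for PWB with one blank:

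- All six answers 2: printed (28 − 12) × 7/6 = 18.67; correct value 14. The wrong score is in range.
- All six answers 0: printed 28 × 7/6 = 32.67, on a scale that ends at 28.

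The highest scores the half-items rule lets through are PWB 28 × 7/4 = 49, EWB 24 × 6/3 = 48 and HBS 72 × 18/9 = 144.

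**Effect on the 5-point cut-off under (a).** The true change needed to count as a responder becomes:

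| Blanks | At follow-up only | At baseline only |
|---|---|---|
| One in HBS (HBS row) | 5 − 4.24 = 0.76 | 5 + 4.24 = 9.24 |
| One in each of PWB and HBS (TOI row) | 5 − 8.90 = −3.90 | 5 + 8.90 = 13.90 |

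Blanks that match in number and kind at both visits cancel in the change score. A blank positively worded item is prorated correctly: EWB with GE2 blank and all other answers 2 gives (20 − 10) × 6/5 = 12.0 either way.

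**Reading (b): a blank makes the expression missing.** A form with six of seven PWB items answered gets no PWB score, although it passes the half-items rule easily. The factor n/(number answered) can then never differ from 1, so it would have no purpose.

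**Exposure (assumption).** The documents give no item-missing rate. The table assumes each item is blank independently with probability p.

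| Share of forms affected | p = 1% | p = 2% | p = 5% |
|---|---|---|---|
| (a) HBS inflated, 1 − (1 − p)^14 | 13% | 25% | 51% |
| (a) TOI inflated, 1 − (1 − p)^21 | 19% | 35% | 66% |
| (b) HBS missing, 1 − (1 − p)^18 | 17% | 30% | 60% |
| (b) TOI missing, 1 − (1 − p)^32 | 28% | 48% | 81% |

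The exponents are 14 reverse-scored HBS items; 14 + 7 for HBS and PWB together; all 18 HBS items; and 7 + 7 + 18 for all TOI items.

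**The case against.** The strongest reply is that the SAP names the FACT-Hep Scoring Guidelines, and that the half-items rule and the proration factor together signal the intended method. A programmer who follows the guideline might reverse item by item and never meet the problem. That is possible, and nothing here shows that the analysis code is wrong. But section 7.8.1 says the guideline is applied through the formulas listed there, and section 7.8 presents them as the scoring algorithms. They are the only specification in the documents, and code validated against them would be checked against a wrong rule.

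A second reply is that blanks will be few. The research associate checks each form and prompts for omissions. The one item the form itself invites patients to skip, GS7, belongs to social/family well-being, which has no constant and does not enter HBS or TOI. This is fair and lowers exposure. The assumed rates above have no source in the documents and should not be read as forecasts. Still, the check ends with refused items being accepted, and the protocol allows completion at home or by mail, where it is harder to apply. Under reading (b), a skipped GS7 would also void the social/family score and the FACT-G and FACT-Hep totals.

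Two further limits stand. Table 41's headline row requires a 5-point gain on both HBS and TOI, so the −3.90 and 13.90 cut-offs apply only to its TOI row. With one follow-up blank in each subscale, a false joint responder still needs a true HBS gain of at least 0.76. And the maxima of 49, 48 and 144 need about half the items blank with best answers on the rest, so they show that the formula fails rather than what to expect.

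**Conclusion.** The concern holds. As printed, the PWB, EWB and HBS formulas are correct only for complete forms, or, if blanks are left out, for forms whose only blanks are positively worded items. Otherwise a blank reverse-scored item either adds 4k × n/(n − k) points or voids a subscale the SAP says to score.

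One blank alone stays below 5 points but moves the effective cut-off by almost that much. Two HBS blanks (9.0), or one in each of PWB and HBS (8.90 on TOI), exceed it with no true change. The results exposed are the QoL scores, change scores and responder proportions in SAP Tables 39 to 41. EWB reaches only its own score and the FACT-G and FACT-Hep totals. The primary pain endpoint is not touched.

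The per-form errors are exact arithmetic. How many forms are affected, and whether the arms differ, cannot be determined from the documents. This should be fixed before the QoL analysis is run.

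**What to change.** Replace the three formulas in SAP 7.8.1 with one rule: subscale score = [sum over answered items of (4 − x) if reverse-scored, or x if positively worded] × (number of items)/(number answered). State that blanks are left out of the sum, and keep the half-items rule. Confirm that the scoring code does this.

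Check the item labels at the same time. The formulas print CP3, CS3 and CF3, whereas the questionnaire has GP3 ("Because of my physical condition, I have trouble meeting the needs of my family"), GS3 and GF3. This may be only a typing or PDF-reading error.

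Report the number of partly answered subscales by arm and visit, so that a reader can see how much rests on proration. A range check (28, 28, 24, 28 and 72 for PWB, social/family, EWB, FWB and HBS) is a useful second safeguard but cannot replace the correction, because inflated scores can stay in range, as the PWB score of 18.67 does.

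The cost is SAP wording and a few lines of code. No new data are needed and patients are not affected.
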